5.2 Primary Efficacy Endpoints

Not applicable.

5.3 Secondary Efficacy Endpoints

SAD and Single dose expansion

Categorical endpoint:

- Complete closure of Tympanic Membrane Perforation (TMP) at Week 8 for SAD and at Week 12 for single dose expansion

TMP complete closure observed response:

Using the non-missing result of complete closure of TMP, an observed response is

Yes: if a subject with complete closure of TMP,

No: if the above condition is false.

TMP complete closure imputed response at Week 8 for SAD:

Using the non-missing result at Week 8, an imputed response is same as observed response at Week 8.

If a response is missing at Week 8, assign the latest post baseline observed response available prior to Week 8.

TMP complete closure imputed response at Week 12 for single dose expansion (Primary analysis imputation):

For endpoint #1 defined in Section [5.3.2](#), using the non-missing result at Week 12, an imputed response is

No intercurrent events (ICE) occurs: same as observed response at Week 12,

ICE occurs: assign the latest post baseline observed response available just before the ICE.

TMP complete closure imputed response at Week 12 for single dose expansion (Sensitivity analysis imputation):

For endpoint #1 defined in Section [5.3.2](#), using the non-missing result at Week 12, an imputed response is

No ICE occurs: same as observed response at Week 12,

ICE occurs: No.

Continuous endpoints:

- Change from baseline in the ratio of TMP size per total area of tympanic membrane at Week 8 for SAD and at Week 12 for single dose expansion

Ratio of TMP size per total area of tympanic membrane (%):

$$[\text{TMP Size} \div \text{Periphery of the Tympanic Membrane Region of Interest (ROI)}] \times 100$$

- Change from baseline in TMP size at Week 8 for SAD and at Week 12 for single dose expansion

Here TMP size = TMP ROI from imaging data.

MAD and Multiple dose expansion

Categorical endpoint:

- Complete closure of TMP at Week 12 for MAD and at Week 16 for multiple dose

expansion

TMP complete closure observed response:

Using the non-missing result of complete closure of TMP, an observed response is

Yes: if a subject with complete closure of TMP,

No: if the above condition is false.

TMP complete closure imputed response at Week 12 for MAD:

Using the non-missing result at Week 12, an imputed response is same as observed response at Week 12.

If a response is missing at Week 12, assign the latest post baseline observed response available prior to Week 12.

TMP complete closure imputed response at Week 16 for multiple dose expansion (Primary analysis imputation):

For endpoint #1 defined in Section [5.3.2](#), using the non-missing result at Week 16, an imputed response is

No ICE occurs: same as observed response at Week 16,

ICE occurs: assign the latest post baseline observed response available just before the ICE.

TMP complete closure imputed response at Week 16 for multiple dose expansion (Sensitivity analysis imputation):

For endpoint #1 defined in Section [5.3.2](#), using the non-missing result at Week 16, an imputed response is

No ICE occurs: same as observed response at Week 16,

ICE occurs: No.

TMP complete closure imputed response at Week 12 for multiple dose expansion:

Using the non-missing result at Week 12, an imputed response is same as observed response at Week 12.

If a response is missing at Week 12, assign the latest post baseline observed response available prior to Week 12.

Continuous endpoints:

- Change from baseline in the ratio of TMP size per total area of tympanic membrane at Week 12 for MAD and at Week 16 for multiple dose expansion
- Change from baseline in TMP size at Week 12 for MAD and at Week 16 for multiple dose expansion

For the change from baseline in the ratio of TMP size per total area of tympanic membrane

and the change from baseline in TMP size, a negative value (decrease from baseline) indicates improvement.

For dose expansion, hypothetical strategy will be applied to analyze the secondary endpoints. Details of ICEs and estimand are shown in Section [5.3.1](#).

5.3.1 Intercurrent Events

Single dose expansion and Multiple dose expansion

1. **Intercurrent events (ICEs):** For the subjects discontinued during the study investigational period, the following ICEs may happen:
 - Randomized but never received study drug
 - Study investigational period discontinuation due to
 - AE
 - Lack of efficacy
 - Lost to follow up
 - Protocol deviation
 - Withdrawal by subject
 - Other
 - Death
2. **Treatment regimen under evaluation:** randomized treatment administered as directed per schedule of assessments.

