2 INTRODUCTION

2.1 Background

Target Disease

Chronic Tympanic Membrane Perforation (CTMP) is defined as stable maintenance of tympanic membrane perforation over 3 months, in contrast to acute tympanic membrane perforations, which heal within 7 to 10 days [Seonwoo et al, 2013]. CTMP affects both pediatric and adult patients and can result from disease, trauma, or medical procedures. Due to the continuous opening in the tympanic membrane, chronic perforation is usually attributed to chronic inflammation in the middle ear, resulting in suppurative otitis media [Seonwoo et al, 2013; Aggarwal et al, 2006]. Surgical repairs such as myringoplasty or tympanoplasty are employed and are currently the main treatments for patients with CTMP. Successful tympanic membrane closure rates vary between studies, ranging from 35% to 99% [Aggarwal et al, 2006]. Disadvantages associated with these surgical procedures include anesthesia-associated risks and the inconvenience of surgery. Therefore, a non-invasive treatment is desired in order to address the unmet need.

ASP0598 and Its Pharmacological Concept

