3.2.1 Intercurrent Events

The following ICEs may happen:

- Treatment discontinuation due to any reason
- Study discontinuation due to any reason

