6.5 Previous and Concomitant Treatment (Medication and Nonmedication Therapy)

These restrictions are required after ASP0598 Otic Solution or placebo administration on Randomization (Day 1), until completion of study procedures at Day 57 (SAD) / Day 85 (single dose expansion or MAD) / Day 113 (multiple dose expansion) or EOS visit.

- Ear drop agents will be used only for the treatment of otitis media with suppurative ear discharge. Only Ciprofloxacin or Ofloxacin ear drops (does not include steroids) are allowed to be used in the ASP0598 Otic Solution or placebo treated ear. Investigators should minimize treatment with ear drops up to a maximum of 10 days and consider alternative treatment (e.g., oral antibiotics).
- Any other topical agents in the ear canal are prohibited to use in the ASP0598 Otic Solution or placebo treated ear.
- Any otologic procedures (e.g., paper patch or surgeries) to the ASP0598 Otic Solution or placebo treated ear are prohibited.

All concomitant medication usage will be noted and recorded during each study visit.

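### A prohibited otologic procedure on the treated ear is not an intercurrent event, so a closure obtained by it could be counted as a response

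*SAP*

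**What the plan says.** **Prohibition.** Protocol 6.5, repeated in 12.6: "Any otologic procedures (e.g., paper patch or surgeries) to the ASP0598 Otic Solution or placebo treated ear are prohibited". A separate bullet covers other topical agents.

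**ICE lists.** Protocol 3.2.1 has two entries: "Treatment discontinuation due to any reason" and "Study discontinuation due to any reason". SAP 5.3.1 opens with "For the subjects discontinued during the study investigational period, the following ICEs may happen" and then lists never being dosed, ending the investigational period for one of six reasons (protocol deviation among them), and death. Treatment discontinuation is in the protocol list but not in the SAP list.

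**Closure rule.** For single dose expansion, SAP 5.3 states "No intercurrent events (ICE) occurs: same as observed response at Week 12". Multiple dose expansion has the same rule at Week 16. After an ICE, the primary imputation takes the last observed status before it, and the sensitivity imputation sets the response to No.

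**Size endpoints.** SAP 5.3.2 drops data from the MMRM only from an ICE onward.

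**Estimand.** Protocol 3.2.2–3.2.3 and SAP 5.3.1–5.3.2 evaluate the randomized treatment given per schedule, with a hypothetical strategy for ICEs.

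**Other handling.** Excluded concomitant treatment is deviation PD4, which is summarised (protocol 9.9 and 10.3, SAP 6.2.2). Whether the subject continues is decided case by case (protocol 10.3). The FAS (SAP 4.1) has no exclusion for it, and no per-protocol set is defined.

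**The concern.** A hypothetical strategy for treatment given as scheduled asks what the ear would have done on the assigned product alone. A membrane closed by a patch or an operation does not answer that question. The plan recognises these as perforation treatments: protocol 2.1 calls surgical repair the main current treatment, and SAP 6.2.3 records earlier paper patching of the treated ear as a baseline characteristic. Yet the response definition in SAP 5.3 asks only whether the membrane is closed, not how it closed.

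Complete closure is the endpoint that sized the expansion and the only one under hierarchical testing. With 13 subjects per arm, one or two misattributed closures can matter. Deciding how to treat them after unblinding would be a post hoc choice.

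**Working it through.** **1. Tracing a subject through the rules**

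| Situation | ICE? | Primary closure analysis | Sensitivity closure analysis | MMRM |
|---|---|---|---|---|
| Procedure, stays in | None on either list | Observed Week 12/16 status | Same observed status | Post-procedure sizes used |
| Procedure, later withdrawn | The withdrawal, not the procedure | Last status before withdrawal; can be a closure seen after the procedure | No | Sizes between procedure and withdrawal used |
| Procedure also stops dosing, stays in (multiple dose only) | Protocol yes, SAP no | Depends on which list governs | Depends on which list governs | Depends on which list governs |

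The third row is narrow. Protocol 8.1 makes treatment discontinuation not applicable to single dose expansion. In multiple dose expansion the last dose is on Day 29 and follow-up runs to Day 113, so for 113 − 29 = 84 days there is no dosing left to stop.

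In the second row, protocol 4.1 has early terminators complete end-of-study (EOS) assessments at discontinuation. The SAP does not say whether that reading precedes the ICE.

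**2. The plan's own figure**

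Inputs (protocol 9.1, SAP 3): closure 10% vs 80%, two-sided 0.05, more than 90% power, 11 per arm, 10% dropout, 13 enrolled. The test behind the calculation is not named. Full enumeration with Fisher's exact test gives power of 84.1% at 10 per arm and 90.5% at 11. Then 11/0.90 = 12.2, rounded up to 13. The figure reproduces, and adding an ICE does not change it.

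**3. Size of one case**

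1/13 = 7.7 percentage points.

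**4. Effect on the test, using the SAP 6.4.2 test choice**

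Assumptions: all 13 per arm analysed; one stratum, because the split by perforation size is unknown; 0 to 2 cases shown, with four added for contrast. With a active closures and m closures in total:

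- E = m/2 and V = 13·13·m(26 − m)/(26²·25) = m(26 − m)/100
- Q = (a − E)²/V on 1 df
- Mantel–Fleiss distance = min(E − L, U − E), with L = max(0, m − 13) and U = min(13, m). MH applies if this is at least 5; otherwise Fisher.

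| Active vs placebo | Distance | Test | p |
|---|---|---|---|
| 8 vs 1 | 4.5 | Fisher | 0.011 |
| 8 vs 2 | 5.0 | MH, Q = 3²/1.60 = 5.63 | 0.018 |
| 8 vs 3 | 5.5 | MH, Q = 2.5²/1.65 = 3.79 | 0.052 |
| 10 vs 1 | 5.5 | MH, Q = 4.5²/1.65 = 12.27 | 0.0005 |
| 10 vs 3 | 6.5 | MH, Q = 3.5²/1.69 = 7.25 | 0.007 |
| 10 vs 5 | 5.5 | MH, Q = 2.5²/1.65 = 3.79 | 0.052 |

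Design rates correspond to 0.80 × 13 = 10.4 and 0.10 × 13 = 1.3 closures, so the 10 vs 1 row is the one close to plan. There, two placebo cases leave the result significant and four are needed to lose it. At 8 vs 1 (62% active closure), two are enough.

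The opposite direction uses the same rows: if 8 vs 3 is the truth and two active non-closers are closed by a procedure, the analysis sees 10 vs 3 and p moves from 0.052 to 0.007.

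**The case against.** **What stands.** The procedures are prohibited, no document gives a frequency, and with no cases nothing changes. The sponsor must be told of a major deviation and may end participation. Discontinuation for protocol deviation is already a listed ICE, and the sensitivity imputation then sets the response to No. Efficacy is secondary here; the primary endpoints are safety. Central readers assess closure under an Independent Review Charter that is not among the documents (protocol 7.1.1) and might address a visible patch. It is therefore right to say that such a closure could be counted, not that it will be.

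**Stronger readings that a reader might infer, and why they fail.**

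- *Prohibited topical agents raise the same problem.* Protocol 6.5 says "Any other topical agents in the ear canal are prohibited to use in the ASP0598 Otic Solution or placebo treated ear" but gives no reason for this or for the ban on procedures, and nothing in the documents shows that such an agent closes a perforation.
- *A patch closes the ear as often as surgery does.* The protocol 2.1 statement, "Successful tympanic membrane closure rates vary between studies, ranging from 35% to 99" percent, concerns surgical repair, not patches.
- *Withdrawing the subject does not help.* It corrects the sensitivity analysis. Only the primary imputation and the MMRM remain exposed.
- *Open placebo ears will be the ones treated, so the bias is toward no difference.* This is plausible if closure is near 10% vs 80%, but it is not documented, and the arithmetic allows either direction.
- *Fisher's p = 0.11 applies at 8 vs 3.* On the single-stratum check the Mantel–Fleiss criterion is met, so the SAP would report the MH result, 0.052.

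**What does not stand.** The possibility of removal does not close the gap. Continuation is decided case by case, and for a subject who stays, no rule in the protocol or SAP changes the response or cuts the size data.

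**Conclusion.** The concern holds for otologic procedures on the treated ear. As written, a subject who has one and remains in follow-up is analysed as though it had not happened, in the primary and sensitivity closure analyses and in the MMRM. If the subject is withdrawn, the primary closure analysis can still carry forward a closure seen between the procedure and the withdrawal. This contradicts the stated estimand; it is more than missing detail.

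The size is 7.7 points per case. Two cases could change the conclusion at a moderate effect but not at one near the design assumption. This rests on 13 analysed per arm, a single stratum and an assumed number of cases. The direction depends on which arm the cases fall in. Because the event should be rare and the endpoint is secondary, this is a should-fix.

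**What to change.** 1. In protocol 3.2.1 and SAP 5.3.1, add as an ICE the first otologic procedure on the treated ear, dated at its occurrence whether or not the subject stays in the study.
2. In SAP 5.3, use the last closure status before that date in the primary imputation and No in the sensitivity imputation, at Week 12 (single dose) and Week 16 (multiple dose).
3. In SAP 5.3.2 and 6.4.2, exclude from the MMRM all perforation size and ratio values after that date, including an EOS visit that follows the procedure.
4. Do not extend the rule to prohibited topical agents without evidence that they affect closure; report those as PD4.
5. In the same edit, reconcile treatment discontinuation, which is an ICE in protocol 3.2.1 but absent from SAP 5.3.1.

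The cost is wording, to be settled before unblinding. Concomitant treatment, PD4 and visit dates are already part of the planned data; confirm that the procedure date is captured. The sample size is unchanged. The downside is that a few observed post-procedure values are not used.

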5.3.2 Estimand

Population: defined by the appropriate inclusion/exclusion criteria in the protocol.

Efficacy endpoints:

3. Complete closure of TMP at Week 12 for single dose expansion and Week 16 for multiple dose expansion.
4. Change from baseline in the ratio of TMP size per total area of tympanic membrane at Week 12 for single dose expansion and Week 16 for multiple dose expansion.
5. Change from baseline in TMP size at Week 12 for single dose expansion and Week 16 for multiple dose expansion.

Strategy for addressing ICEs: hypothetical strategy will be used to estimate the outcome at Week 12 for single dose expansion and Week 16 for multiple dose expansion.

Population-level summary:

- **Endpoint #1 (Categorical):** difference in proportion of subjects with complete closure of TMP at Week 12 for single dose expansion and Week 16 for multiple dose expansion between ASP0598 and placebo.
- **Endpoint #2 (Continuous):** difference in mean change from baseline in the ratio of TMP size per total area of tympanic membrane at Week 12 for single dose expansion and Week 16 for multiple dose expansion between ASP0598 and placebo.

- **Endpoint #3 (Continuous):** difference in mean change from baseline in TMP size at Week 12 for single dose expansion and Week 16 for multiple dose expansion between ASP0598 and placebo.

Data that will be used for the estimand:

- **Endpoint #1:** data necessary for this estimand is complete closure status at Week 12 for single dose expansion and Week 16 for multiple dose expansion. For the subjects discontinued during the study investigational period with ICEs, the complete closure status just before the ICE will be used as the status at Week 12 for single dose expansion and Week 16 for multiple dose expansion.
- **Endpoints #2 and #3:** data necessary for these estimands are TMP size per total area of tympanic membrane and TMP size at each visit, respectively. For the subjects discontinued during the study investigational period with ICEs, only data obtained before the ICE will be used in the Mixed model repeated measures (MMRM) to handle discontinued subjects in some sense if the subjects remained in the study under missing at random (MAR) assumption.

5.4 Exploratory Endpoints

Single dose phase:

- Complete closure of TMP for post baseline visits at Day 2, Day 3 (evaluations at this visit will only be performed for cohorts 1, 2 and 3), Week 1, Week 2 and Week 4 for SAD and Week 2, Week 4 and Week 8 for single dose expansion
For the observed response definition, refer to Section [5.3](#).
- Change from baseline in the ratio of TMP size per total area of tympanic membrane for post baseline visits at Day 2, Day 3 (evaluations at this visit will only be performed for cohorts 1, 2 and 3), Week 1, Week 2 and Week 4 for SAD and Week 2, Week 4 and Week 8 for single dose expansion
- Change from baseline in TMP size for post baseline visits at Day 2, Day 3 (evaluations at this visit will only be performed for cohorts 1, 2 and 3), Week 1, Week 2 and Week 4 for SAD and Week 2, Week 4 and Week 8 for single dose expansion

Multiple dose phase:

- Complete closure of TMP for post baseline visits at Week 1, Week 2, Week 3, Week 4, Week 5 and Week 8 for MAD and Week 2, Week 4, Week 6, Week 8 and Week 12 for multiple dose expansion

For the observed response definition, refer to Section [5.3](#).

- Change from baseline in the ratio of TMP size per total area of tympanic membrane for post baseline visits at Week 1, Week 2, Week 3, Week 4, Week 5 and Week 8 for MAD and Week 2, Week 4, Week 6, Week 8 and Week 12 for multiple dose expansion

- Change from baseline in TMP size for post baseline visits at Week 1, Week 2, Week 3, Week 4, Week 5 and Week 8 for MAD and Week 2, Week 4, Week 6, Week 8 and Week 12 for multiple dose expansion

Single and multiple dose phases:

- Time to closure of TMP

Time to closure of TMP (days):

TMP closure date - first dose date + 1. If the TMP is not closed, then time to closure will be set to missing.

- Size of TMP $\leq 5\%$ of pars tensa surface area after treatment

Observed response:

Using the non-missing size of TMP per pars tensa surface area, an observed response is

Yes: if the post baseline size of the TMP per pars tensa surface area $\leq 5\%$ and the size of the TMP per pars tensa surface area is smaller than baseline,

No: if the above condition is false.

Ratio of TMP size per total area of tympanic membrane will be used in the above calculation as an approximation for TMP per pars tensa surface area.

- Size of TMP $\leq 1\%$ of pars tensa surface area (pin point perforation) after treatment

Observed response:

Using the non-missing size of TMP per pars tensa surface area, an observed response is

Yes: if the post baseline size of the TMP per pars tensa surface area $\leq 1\%$ and the size of the TMP per pars tensa surface area is smaller than baseline,

No: if the above condition is false.

Ratio of TMP size per total area of tympanic membrane will be used in the above calculation as an approximation for TMP per pars tensa surface area.

- Change from baseline in Air bone (A-B) gap by PTA

For the change from baseline in A-B gap, a negative value (decrease from baseline) indicates an improvement.

PTA is a behavioral test and generally the 1st quantitative hearing test done to assess the nature and degree of hearing loss in adults and in children.

PTA air conduction and bone conduction tests analyzed together determines any hearing loss: type and magnitude of hearing loss; frequencies that are affected; and whether hearing loss is unilateral or bilateral. For both air and bone conduction, a lower value indicates better hearing threshold.

Type of hearing loss can be as follows:

- Conductive hearing loss: when air conduction thresholds are elevated relative to bone conduction thresholds, an “A-B gap” exists, indicates a conductive hearing loss.
- Sensorineural hearing loss: when air conduction and bone conduction thresholds showing the same amount of hearing loss, indicates sensorineural hearing loss.
- Mixed hearing loss: when both air and bone conduction thresholds are elevated, but air conduction thresholds are more elevated than bone conduction thresholds, indicates mixed hearing loss.

Definitions for mean bone conduction hearing, mean air conduction hearing, mean A-B gap and A-B gap (dB) for each frequency are provided below:

Mean bone conduction hearing (dB):

Arithmetic mean of the bone conduction hearing values at 500 Hz, 1, 2 and 4 kHz. If the value is missing for any of the 4 frequencies, then the mean value will be set to missing.

Mean air conduction hearing (dB):

Arithmetic mean of the air conduction hearing values at 500 Hz, 1, 2 and 4 kHz. If the value is missing for any of the 4 frequencies, then the mean value will be set to missing.

Mean A-B gap (dB):

Mean air conduction hearing - mean bone conduction hearing. If either one is missing or both are missing then the mean A-B gap is set to missing.

A-B gap (dB) for each frequency:

Air conduction hearing at the frequency level - bone conduction hearing at the frequency level. If either one is missing or both are missing then the A-B gap is set to missing. This will be derived for frequencies 500 Hz, 1 kHz, 2 kHz, and 4 kHz.

- Change from baseline in air conduction hearing by PTA

Mean air conduction hearing will be derived as explained in the endpoint Percentage improvement from baseline in A-B gap by PTA $\geq 50\%$ (improvement of conductive hearing)

- Percentage improvement from baseline in A-B gap by PTA $\geq 50\%$ (improvement of conductive hearing)

Observed response:

Using the non-missing percentage change from baseline in mean A-B gap, an observed response is

Yes: if the percentage change from baseline in mean A-B gap (derived using mean of the A-B gap results at 500 Hz, 1, 2 and 4 kHz) $\leq -50\%$,

No: if the above condition is false.

- Improvement from baseline in air conduction hearing by PTA ≥ 15 dB
For the change from baseline in air conduction hearing, a negative value (decrease from baseline) indicates an improvement.

Observed response:

Using the non-missing change from baseline mean air conduction hearing, an observed response is

Yes: if the change from baseline in mean air conduction hearing by PTA ≤ -15 dB,
No: if the above condition is false.

- A-B gap after treatment was 15 dB or less

Observed response:

Using the non-missing mean A-B gap, an observed response is

Yes: if the post baseline mean A-B gap ≤ 15 dB,
No: if the above condition is false.

- Air conduction hearing threshold after treatment was 30 dB or less

For the air conduction hearing, a lower value indicates better hearing threshold.

Observed response:

Using the non-missing mean air conduction hearing, an observed response is

Yes: if the post baseline mean air conduction hearing ≤ 30 dB,
No: if the above condition is false.

- Type of tympanogram (A, B or C)
For Type A, there are 2 additional subcategories: Ad and As.
- Equivalent ear canal volume (ECV) by tympanometry

Safety endpoint:

- Vital signs (body temperature, blood pressure and pulse rate)
- Microscopic ear examination

At screening, both ears will be examined microscopically to identify the TMP and evaluate the eligibility of the subject for the study. Only treated ear will be examined at Day 1 and the following visits.

On Day 1, Week 2 (multiple dose only), and Week 4 (multiple dose only), 1 h after the treatment, the following ear canal reactions of treated ear will be collected.

Did the ear experience an abnormal ear sensation

- No

- Yes
 - Burning
 - Stinging
 - Itching
 - Pain
 - Other

After Day 1, data for the following parameters will be collected:

- Gel visible in the treated ear (Yes, No)
- Gel visible in the middle ear (Yes, No)
- TMP of treated ear completely closed (Yes, No, Unknown)
- Ear pain (otalgia) in the treated ear (Yes, No)
- Status of the treated tympanic membrane (Normal, Abnormal, Abnormal: Myringitis, Abnormal: Hematoma, Abnormal: Other, Not visible)
- Status of the middle ear in the treated ear (Normal, Abnormal, Abnormal: Mucosal inflammation with effusion, Abnormal: Mucosal inflammation without effusion, Abnormal: Other, Not visible)

Local skin reaction around the application site will be examined at 60 minutes after the treatment at Day 1 and throughout the observation period. Skin toxicity will be evaluated by Modified Brighton Grading Scheme as shown below.

Grade	Description
0	no abnormalities
1	canal erythema
1b	canal erythema with otorrhea (ear canal fluid discharge)
2	canal erythema + swelling, TM still visible
2b	canal erythema + swelling, TM still visible with otorrhea
3	canal erythema + swelling, TM not visible
3b	canal erythema + swelling, TM not visible with otorrhea
4	canal erythema + swelling, TM not visible + erythema and swelling of the pinna
4b	canal erythema + swelling, TM not visible + erythema and swelling of the pinna with otorrhea

Pharmacokinetics:

- Serum concentration of ASP0598 (dose escalation part only)

